## 5.2. Masking

This is a subject-masked study. Masking will be used to reduce potential bias. Subjects will be unaware of the identity of the investigational product. Investigators and clinical site personnel involved in the data collection will not be masked as to the identity of the investigational product. Although the subjects will not be aware of which study lens is going on which eye, the dynamic nature of the test lens during the assessments may give the identity.

Under normal circumstances, the mask should not be broken until all subjects have completed the study and the database is finalized. Otherwise, the mask should be broken only if specific emergency treatment/course of action would be dictated by knowing the treatment status of the subject. In such cases, the Investigator may, in an emergency, contact the medical monitor. In the event the mask is broken, the Sponsor must be informed as soon as possible. The date, time, and reason for the unmasking must be documented in the subject record. The Investigator is also advised not to reveal the study treatment assignment to the clinical site or Sponsor personnel.

Subjects who have had their treatment assignment unmasked are expected to return for all remaining scheduled evaluations. Subjects who are discontinued will be replaced.

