#### 2.3. Hypotheses

Primary Hypotheses (each is considered independent)

- 1. Light Scattering
  - a. The Test lens (in the absence of an additional UV/HEV light source) will be statistically lower than the Control lens with respect to light scattering as measured using the two-point light threshold instrument.
  - b. The Test lens (in the presence of an additional UV/HEV light source) will be statistically lower than the Control lens with respect to light scattering as measured using the two-point light threshold instrument.

- 2. Haloes
  - a. The Test lens (in the absence of an additional UV/HEV light source) will be statistically lower than the Control lens with respect to halos. This is measured using the halometer instrument.
  - b. The Test lens (in the presence of an additional UV/HEV light source) will be statistically lower than the Control lens with respect to halos. This is measured using the halometer instrument.
- 3. Starbursts
  - a. The Test lens (in the absence of an additional UV/HEV light source) will be statistically lower than the Control lens with respect starbursts as measured using the halometer instrument.
  - b. The Test lens (in the presence of an additional UV/HEV light source) will be statistically lower than the Control lens with respect starbursts as measured using the halometer instrument.

Secondary Hypotheses (each is considered independent)

- 1. The Test lens (in the absence of an additional UV/HEV light source) will be statistically lower than the Control lens with respect to photostress recovery time (seconds) as measured using the optical bench instrument.
- 2. The Test lens (in the absence of an additional UV/HEV light source) will be statistically higher than the Control lens with respect to disability glare threshold as measured using the optical bench instrument.
- 3. The Test lens (in the absence of an additional UV/HEV light source) will be statistically lower than the Control lens with respect to discomfort glare (eyelid squinting) as measured using the optical bench instrument.
- 4. The Test lens (in the absence of an additional UV/HEV light source) will be statistically higher than the Control lens with respect to chromatic contrast threshold than as measured using the optical bench instrument.

Other Hypotheses

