## 4.2. Study Design Rationale

This study will be executed using a contralateral design. There are several benefits to this choice of design. First, we intend to relate performance with the investigational lens in its activated and inactivated states to baseline light sensitivity. A contralateral design will allow us to compare performance with both activation states within the same individual, ostensibly with the same baseline light sensitivity. Second, other subject factors that can influence visual performance, such as iris color and absorption of test lights via macular pigment, are better controlled using this design. Third, in psychophysical testing, which is the gold standard for many of the visual functions being tested, participants make judgments about some event threshold, such as when an image disappears or how large or bothersome or intense a visual event appears. Participants may have different criteria for threshold events that are internally consistent *within* subjects but can vary *between* subjects. A contralateral design allows the investigational lens to be compared within subjects, with consistent criteria for threshold events. Given the fact that sufficient time will be taken between measures, in some cases 24 hours or more, carryover effects are unlikely.

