## 5. TEST ARTICLE ALLOCATION AND MASKING

## 5.1. Test Article Allocation

Use of the test articles will be randomized using a randomization scheme supplied by the study biostatistician.

This is a single-site, two-visit, contralateral, subject-masked, non-dispensing and randomized study. The study lenses will be worn in a contralateral and random fashion. At visit 1, a block size of (2) sequences will be used to randomly assign subjects to one of two lens wear sequences (Left: Test, Right: Control or Left: Control, Right: Test).

At visit 2, there are two levels of randomization, a block size of (2) sequences will be used to randomly assign subjects to one of two lens wear sequences (Left: Test, Right: Control or Left: Control, Right: Test). Once subjects are randomized to a lens wear sequence, subjects will then be randomized to the order of Test lens activation (activated/inactivated or inactivated).

The random scheme for each visit will be generated by site using the PROC PLAN procedure from SAS Software Version 9.4 or higher (SAS Institute, Cary, NC).

The study site must follow the randomization scheme provided and complete enrollment according to the randomization list and not pre-select or assign subjects. The randomized assignment of subjects will be performed at the first visit prior to the first fitting. The following must have occurred prior to randomization:

- Informed consent has been obtained
- Subject meets all the inclusion / exclusion criteria
- Subject history and baseline information has been collected

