#### The background

The background channel will be manipulated to produce either an annulus (for GDs) or a three-degree background field (for GDc and PR). For the HCT test, the same three-degree background will be filtered through a 460 nm interference filter (half-power bandwidth = 8 nm; Edmund Optics; Barrington, NJ) in order to produce a monochromatic field. Xenon was selected as the light source because it has the characteristic broad band emission spectrum (as assessed by the SpectraScan colorimeter) with a CIE chromaticity of u' = 0.25, v' = 0.53. Xenon is widely regarded as a good match for sunlight. For example, in a study of 26 solar simulators, the authors noted that xenon-arc light sources match the most accurately. The xenon spectrum that will be produced by this system is shown in Figure 4 as compared to mid-day sunlight.

JJVC CONFIDENTIAL

[figure not shown]

Figure 4: The xenon (dark line) compared to noon day sun light (red line). The line in red is taken from the NASA solar spectrum measured at the earth's surface  and adjusted along the ordinate with respect to the xenon source that will be used in this study.

JJVC CONFIDENTIAL

	Psychophysical Testing A: Photostress / Glare / Chromatic Contrast		
Т	The psychophysical tests described in Steps 1-4 below may occur in any order. No additional UV/HEV activation light source will be used.		
Step	Procedure	Details	
1	Glare Disability (GDs)	The target stimulus will be presented for 2 seconds on and 1 second off to reduce the chances that subjects will habituate to the stimulus. A second channel will provide an annulus with an approximately 11-degree inner diameter and 12-degree outer diameter, as shown below.	
		Before each trial, the annulus will be set at a level well below that which would cause the target stimulus to be veiled. The experimenter will then adjust, via the neutral-density wedge, the intensity of the annulus until the target stimulus is no longer visible. Participants will indicate that the target has been veiled by pressing a buzzer.	
		The experimenter increases the intensity of light scattering within the subjects' test eyes until they cannot effectively see. Unlike the photostress bleach which is set and standard, the intensity is varied in this test, and hence, so is the aversiveness of the dependent variable. This measurement has been conducted successfully, repeatedly, in the past 	

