2	Heterochromatic Contrast Threshold (HCT)	Chromatic contrast will be measured as thresholds to a variable wavelength central target presented on a short-wave (460 nm) sky-light background. This aspect of the testing is mostly exploratory to see how the contacts influence chromatic contrast. The relation to filtering is very strong as long as there is differential filtering between the target and the background.	
		Stimulus size Stimulus size	

Page 39 of 117

	Psychophysical Testing A: Photostress / Glare / Chromatic Contrast			
3	Photostress Recovery (PR)	To measure PR time, participants are exposed to the same target used in each of the other visual function tests. Once the participant is comfortably viewing the target, the experimenter will cover the target with a bright, bleaching light. Exposure to the light will cause participants to momentarily lose sight of the target, which will be covered by an afterimage. As the afterimage fades, participants will gradually be able to re-gain sight of the target. PR time will be recorded as the time it takes following exposure to the bleaching light to regain sight of the target.		
4	Glare Discomfort (GDc)	
 
Glare discomfort (GDc) will be quantified using the squint response and a questionnaire. The discomfort that accompanies exposure to light in excess of an individual's adaptive state is accompanied by contraction of the extraocular muscles (squint). The squint response has been shown to be a valid objective indicator of glare discomfort. This procedure was described by Gowrisankaran. Degree of squint is calculated as the ratio of the height of the palpebral fissure under normal lighting conditions compared to maximal squint produced during the photostress exposure. A high-resolution camera (AmScope MU300 digital camera; Irvine, CA) will be used and calibrated against a spatial standard before the start of each day of testing. The resultant videos will be analyzed as still frames using AmScope measurement software (Irvine, CA). To determine subjective ratings of GDc, subjects will be asked to rate the degree of discomfort of the photostressor using a single-item questionnaire OD and OS:
 
How bothersome was the glare that you just experienced? Subjects will have the following response options: Extremely bothersome, Very bothersome, Somewhat bothersome, A little bothersome, Not at all bothersome.
 
		

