#### Investigational contact lenses

The investigational lenses will be tested with an additional UV/HEV light source as one of the test conditions. "Activation" will be achieved using an ultraviolet activator consisting of LEDs waveband 365-400 nm that combines with the primary optical path of the system, after the final lens of the optical system (see Figure 7). The spectral output of the ultraviolet LEDs is given in Appendix G. The ultra-violet LEDs will be used, at a low constant rate, while the visual measures (halos, etc.) are being collected. The overall energy at the plane of the eye is 64  $\mu$ w/cm2 (measured using the ILT 950, the graph in Appendix G is the light source at the energy we plan to use during the measurement). As a comparison, the UV activator emits 0.07 mw/cm2 whereas mid-day sunlight measured 11 mw/cm2 using the same instrument (1:00 PM, partially cloudy day, September 18, 2017, Athens, GA using a UVA light meter: General UV254SD).

JJVC CONFIDENTIAL

JJVC CONFIDENTIAL

	Psychometric Testing B: Dysphotopsia Evaluation			
	The psychophysical tests described in Steps 1-3 below may occur in any order. All three tests will perfomed twice: once with an UV/HEV activating light source and once with no activating light source. The order of light source testing will be randomized.			
Step	Procedure	Details		
1	Two-point Light Spread Function	These thresholds are defined as the minimum distance that two points of light are completely distinct. An ascending and a descending method of limits will be used. This measurement takes about 10-15 minutes. Record values OD and OS, in mm (2 decimal places).		
2	Starburst	This is defined as the diameter of the light's lateral spread. Subjects will have the nature of starbursts explained using visual aids prior to the experiment. The investigator will adjust a calibrated custom-made micrometer (two sides with reverse threading) to spread two posts out from a central mid-point. Those posts will be used to define the outer boundaries of the starburst image. Ascending and descending methods of limits would be used based on subject feedback. This measurement takes about 10-15		

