		Calipers are adjusted until the inner edges are just touching the edges of the starburst pattern. minutes. Record values OD and OS, in mm (2 decimal places). Subjects will respond to a single-item post- starburst questionnaire OD and OS: • How severe / intense was the starburst that you experienced? Subjects will have the following response options: Severe, moderate, mild, not at all.		

	Psychometric Testing B: Dysphotopsia Evaluation				
	The psychophysical tests described in Steps 1-3 below may occur in any order. All three tests will perfomed twice: once with an UV/HEV activating light source and once with no activating light source. The order of light source testing will be randomized.				
Step	Procedure	Details			
3	Halos	Subjects will have the nature of halos explained using visual aids prior to the experiment. The halo measurement will utilize the same light source as the starburst and two- point measures to produce the halo. The same calibrated micrometer from the starburst test will be used to define the outer edges of the halo image (investigator adjusting based on subject feedback). Ascending and descending methods of limits will be used. This measurement takes about 10-15 minutes. Record values OD and OS, in mm (2 decimal places). Subjects will respond to a single-item post-halo questionnaire OD and OS:			
		• How severe / intense was the halo that you experienced? Subjects will have the following response options: Severe, moderate, mild, not at all.			
4	Repeat	The steps above will be repeated but with the alternate light source testing method. The investigator must allow at least 10 minutes to lapse before starting the second round of testing.			

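### Section 5.2 leaves every examiner unmasked although key endpoints are set by hand; keeping the lens assignment from the existing co-investigator tester would mask part of the testing at modest cost

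*Combined protocol and SAP*

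**What the plan says.** Section 5.2 describes a subject-masked study and says of everyone else that "Investigators and clinical site personnel involved in the data collection will not be masked as to the identity of the investigational product". It gives no reason for leaving examiners unmasked. It adds that the changing appearance of the Test lens may reveal its identity to the subject.

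Examiners have a hand in several endpoints (Section 7.2):

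- **Starburst** (Testing B, step 2): "The investigator will adjust a calibrated custom-made micrometer (two sides with reverse threading) to spread two posts out from a central mid-point".
- **Halo** (Testing B, step 3): the same micrometer, "investigator adjusting based on subject feedback".
- **Two-point threshold** (Testing B, step 1): no operator is named. Section 2.3 speaks of this endpoint "with respect to light scattering as measured using the two-point light threshold instrument", but the Testing B apparatus text says all three tests share one apparatus, and Section 14.5 (Halos) says halos, starbursts and light scattering share the micrometer.
- **Glare disability** (Testing A, step 1): "The experimenter will then adjust, via the neutral-density wedge, the intensity of the annulus until the target stimulus is no longer visible". The subject signals with a buzzer.
- **Squint** (Testing A, step 4): "The resultant videos will be analyzed as still frames using AmScope measurement software", by a person not named.

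Steps 1.25 and 2.17 have a co-investigator run the testing, after which the subject goes back to the principal investigator. Section 5.3 lets the investigator or any designee read the randomisation scheme, and steps 1.15 and 2.7 let the investigator or the subject insert the lenses. Nothing keeps the assignment from the tester. Section 5.1 prints the block size for Visit 1 and again for Visit 2: "At visit 2, there are two levels of randomization, a block size of (2) sequences will be used to randomly assign subjects".

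**The concern.** The design rationale in Section 4.2 relies on the subject as own control: "A contralateral design allows the investigational lens to be compared within subjects, with consistent criteria for threshold events". That deals with how strictly each subject judges a threshold. It does not deal with the person turning the micrometer or the wedge. An examiner who expects the Test lens to do better, and who knows which eye wears it, can treat the two eyes of one person slightly differently. That difference follows the Test lens, so it enters the paired contrast in full. Randomising left and right does not cancel it.

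Four of the six primary hypotheses (2a, 2b, 3a, 3b) rest on posts that the plan says the investigator sets. The two light-scattering hypotheses (1a, 1b) share the equipment. Section 14.2 reports no historical data for the primary endpoints, so nothing in the documents shows that such a shift would be negligible.

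**Working it through.** The plan gives no SD, effect size or power, so there is no figure of its own to reproduce.

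**Inputs.** 60 completers (14.2). Success on a primary endpoint if the upper limit of the two-sided 95% interval is below 0 (14.5), which leaves 2.5% in the favourable tail. Block size 2 at each visit (5.1). Random activation order (5.1, 7.2). Assumed: a 1:1 order, and examiner shifts *d* of 0.1 or 0.2 SD of the paired difference.

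**1. How much testing could be masked.** Suppose all three Visit 2 tests are done in both lamp rounds and an inactivated Test lens cannot be recognised.

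- Visit 1, no activating lamp: 4 × 60 = 240 tests.
- Visit 2: 3 × 2 × 60 = 360 tests, of which lamp-off-first 3 × 30 = 90 (25%). Lamp-off rounds that follow a lamp-on round are counted as unmasked.
- Total: (240 + 90)/600 = 330/600 = 55%.

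For starburst and halo alone this is 25% of rounds, or half of the lamp-off rounds.

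**2. What blocks reveal.** Suppose the tester knows the block size, has learned the earlier assignments in the block, and can match testing order to list order. For blocks of size 2*m*, the share of assignments fixed by earlier ones is 1/(*m* + 1): 1/2 for blocks of 2 (30 of 60), 1/3 for 4 (20 of 60), 1/4 for 6 (15 of 60).

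Of 30 lamp-off-first subjects, those still masked number 30 if blocks cannot be inferred, 30 × 2/3 = 20 with known blocks of 4, and 30 × 1/2 = 15 with known blocks of 2.

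**3. Illustrative error rates.** The simplified analysis is a one-sample t test on 60 paired differences with SD 1. SE = 1/√60 = 0.129. With nobody masked, the false Test-lower rate is P(T < −t) for a noncentral t with 59 df and noncentrality −*d*√60 (−0.775 or −1.549). The normal approximation Φ(*d*√60 − 1.96) gives 11.8% and 34.1%; the t version gives 11.5% and 33.1%. With *M* pairs masked, the mean shift is *d*(60 − *M*)/60, and the mixture adds *d*²*M*(60 − *M*)/60 to the noncentrality of the sum of squares.

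| Pairs masked (lamp-off) | *d* = 0.1 | *d* = 0.2 |
|---|---|---|
| 0 | 11.5% | 33.1% |
| 15 (known blocks of 2) | 8.2% | 20.5% |
| 20 (known blocks of 4) | 7.3% | 17.0% |
| 30 (blocks not inferable) | 5.7% | 11.4% |

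The partial-masking rows apply to 2a and 3a, and to 1a if the examiner sets the two-point separation. Lamp-on comparisons may stay in the top row. Moving from known blocks of 2 to known blocks of 4 helps less than making the blocks impossible to infer.

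**4. Can the tester work without knowing the Test eye?** The documents point two ways.

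- Section 2.2 and the Testing B apparatus text list three lens conditions, with Control appearing once. Section 5.1 randomises the order of activation of the Test lens.
- The Testing B table has every test done twice, with and without the lamp, and values recorded for each eye.

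If both eyes are tested in both rounds, the tester needs only the activation order. If the lamp is used only for the Test eye, the tester must be told which eye that is, and lamp-on testing cannot be masked.

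**The case against.** **Subject-only masking is disclosed and consistent.** True: this is a design weakness, not an internal error. The warning that the lens may reveal itself is made about subjects, but the same obstacle plausibly faces a tester.

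**The settings follow the subject.** Subject feedback, ascending and descending limits and the buzzer all constrain the examiner. They reduce the influence without excluding it.

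**The remedy reaches least where the concern is greatest.** This stands. Lamp-on comparisons may gain nothing. Even lamp-off-first rounds and Visit 1 depend on the xenon source not tinting the lens visibly; xenon was chosen for Testing A because it resembles sunlight, and Visit 2 uses it too. The documents do not describe how an inactivated Test lens looks on the eye.

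**Block inference is conditional.** A reader might infer that blocks of 2 simply hand the tester every second assignment. The documents do not support that. Visit 2 falls 1 to 28 days after Visit 1, so testing order need not follow list order. At Visit 1, if the inactive lens is unrecognisable, a tester without the list learns nothing to carry forward. Half is an upper limit.

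**Low cost is a judgement.** Nothing says the co-investigator takes no part in lens handling, and there are no staffing data. What stands is that the plan already names a tester distinct from the principal investigator.

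**Conclusion.** The concern holds as a possible and partly avoidable bias. All data collectors are unmasked while starburst, halo and glare disability are adjusted by hand and squint is read from frames. A reader might set the two-point test aside as having its own instrument; the shared apparatus and micrometer do not support that, although its operator is not named.

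Two stronger readings go too far. One is that the results will be biased, or that the error rates in the table estimate the trial's true error. The shifts are assumed, nothing in the documents anchors them, and the calculation simplifies the planned mixed model. The other is that full examiner masking is available. At best about 55% of tests could be masked: all of Visit 1 and the lamp-off-first quarter of Visit 2. That rests on a 1:1 activation order, both eyes tested in both rounds, and an inactivated lens that cannot be recognised. The change is worth making because it needs no new role, not because a distortion has been shown.

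**What to change.** - **Sections 5.2, 5.3 and steps 1.25/2.17:** the principal investigator, or a designee other than the tester, holds the randomisation list and handles, inserts (or oversees self-insertion of) and replaces lenses. The co-investigator tester is not given the lens assignment. Squint frames are coded by subject and eye before measurement; coding will not hide a tint visible in the frame.
- **Section 5.1:** move the block size to a file the tester does not see, and use varying or larger blocks at both visits.
- **Sections 2.2, 5.1 and 7.2 (Testing B):** reconcile whether both eyes are tested in both lamp rounds. If the lamp is used only for the Test eye, say that lamp-on testing at Visit 2 cannot be masked. Name the operator of the two-point test.
- **Section 5.2:** state that examiner masking is partial and where it may fail: lamp-on rounds, rounds that follow them after the minimum 10-minute gap, and wherever xenon light tints the lens.
- **Record** per round whether the tester knew the Test eye. Report it as description only, with no efficacy subset.

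The cost is protocol wording, new lists from the procedure already in use, a handover rule, one recorded item per round, and a lens handler available during testing. Larger blocks can leave a left/right imbalance of at most half the block size: 66 divides evenly by 6 but leaves a part block with 4 or 8.
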